Our 2016-17 data on 202 older adults from 16 publicly subsidized housing units indicates untreated caries (58%) is two times higher than the national average (28%). All had at least one medical condition, while 83% had two or more medical conditions (**RQ-4**). Nationally, 92% of U.S. older adults have at least one medical condition, and 77% have  $\geq 2$  conditions. Low-income U.S. older adults have disproportionately increased medical conditions compared to their more affluent counterparts as shown by our NE Ohio data. Recent studies indicates that poor dental health (caries, periodontitis) was related to worsening glucose tolerance and an increased risk of diabetes, and having fewer teeth/tooth loss and other patient reported oral health problems was associated with greater physical frailty in older adults. Medical conditions lead to less frequent dental visits among older adults with cognitive impairment and those with diabetes, with significant disparities among low-income groups. Moreover, systemic conditions such as cardiovascular and respiratory disease, diabetes etc. have been associated with oral infections. Untreated oral infection leads to pain, overuse of emergency visits, and even death (**RQ-1**).

Despite the profound impact of oral health status on quality of life, many older adults accept their oral health problems as an inevitable process of aging and do not seek dental care. In fact, ADA Health Policy Institute survey indicates that low perceived need (i.e. not needing dental care) was the top reason that older adults do not intend to visit a dentist. This belief, further impacted by limited dental insurance options results in oral health becoming a low priority among older adults. The National Health Interview Survey 2014 data indicate that most older adults reported financial barriers to receiving dental care compared to any other type of health care. A further challenge is that older adults have increased medical problems, physical frailty, and cognitive issues that challenge dental care access in this group. Testing interventions provided outside of traditional dental offices will address barriers to seeking care among this population (**RQ-1, RQ-3**).

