**Moderating Variables will be assessed only at Baseline ( $T_0$ ) through:**

Moderating variables will be collected using the following instruments: a 9-item socio-demographic questionnaire (NHANES III, CDC), a 10-item common chronic health condition for adults 65+ questionnaire (adapted from the Nation Council on Aging(NCOA), a 12-item self-reported measures of current oral disease / tissue damage questionnaire (Gilbert et al., 1997), and a 5-item oral hygiene (adapted from Kuusela, 1997 and WHO) These measures will be considered as potential moderators and will be collected at the baseline visit only.

**Table 8.1.2. Qualitative Focus Study Procedures / Evaluations (to be conducted in year 2, year 3, and year 4 either virtually or at a convenient housing facility, based on housing site circumstances at the time of focus group scheduling)**

Subject	Planning / Design	At the Focus Group Process	Data Collection
Group Participants	
Recruitment
 
 
Participants who will complete the clinical trial randomly invited to one of the three focus group interviews
 
	
Comfortable environment
 
 
Provide signed and dated consent form at the beginning of interview protocol
 
	
Activities
 
 
Generate ideas / efforts to contribution
 
Engagement and input on focus group activity
 

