Heterogeneity of Treatment Effects (HTE: HT-1, HT-2, HT-3). Our primary hypothesis addresses the effect of interventions at 12 months, as well as the longitudinal effect of the interventions. There is no empiric data on comparative effectiveness of these interventions, but individually they have similar effectiveness from prior literature. In particular, we will assess the possible moderators indicated in Figure 1; specific examples include age (e.g., dichotomized as age < 75 versus age  $\geq$  75), presence of two or more medical conditions, gender, and race. Heterogeneity of treatment effect will be assessed by adding to the GEE models each potential moderator, along with the corresponding interaction with treatment. We will test moderator by treatment interactions to determine evidence for subgroup differences in the treatment effect. Corresponding 95% confidence intervals for the treatment effect for each subgroup will be computed. Secondarily, we will conduct an interaction tree approach such as CHAID (Chi-squared automatic interaction detection) an extension of CART (Classification and Regression Trees) to simultaneously assess the set of potential moderators, and determine subgroups that have significant intervention effects.

**Reporting Plan (IR-5):** To allow for assessment of study's internal and external validity, we will adhere to standard reporting guidelines for randomized clinical trials as specified by: EQUATOR network, SPIRIT 2013 statement; and CONSORT 2010 statement.

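### Section 11.4 names only two-group codings for comorbidity and, as an example, age. If the treatment effect is graded, this discards roughly 55–70% and one third of the interaction information.

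*Combined protocol and SAP*

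**What the plan says.** Under Heterogeneity of Treatment Effects, Section 11.4 introduces the moderators as illustrations: "specific examples include age (e.g., dichotomized as age < 75 versus age" 75 or above, followed by "presence of two or more medical conditions, gender, and race". The test is an interaction term: "Heterogeneity of treatment effect will be assessed by adding to the GEE models each potential moderator", together with its product with treatment. A 95% CI for the treatment effect is then reported in each subgroup. A tree method follows: "Secondarily, we will conduct an interaction tree approach such as CHAID". No count-based or continuous form of either moderator is specified, and no power is stated for these tests.

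Finer data are collected. Section 8.1.1 (Moderating Variables) lists "a 10-item common chronic health condition for adults 65+ questionnaire" and "a 9-item socio-demographic questionnaire (NHANES III, CDC"), both at baseline. Section 2.1 reports that in the team's earlier sample of 202 residents everyone had at least one condition and "83% had two or more medical conditions". The Protocol Summary carries the 83% forward as the expected figure. Section 2.2 makes co-existing medical conditions a stated focus.

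**The concern.** Comorbidity is the subgroup question the protocol singles out, yet the coding it names puts about five in six participants into one cell. People with two conditions and people with six become identical, and the contrast rests on the small remainder. If the relative effect of SDF and ART+FV drifts with disease burden, most of that drift lies inside the large cell, where the binary term cannot see it. The age split has the same defect in milder form, because it falls near the expected mean of 74. What is at stake is the sensitivity of the interaction tests, and the risk that a null result is read as evidence of a uniform effect.

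**Working it through.** **Inputs from the documents.** 275 per arm, 25 per site, 15% dropout, SD 25 and margin 8 on pain, arrest rate 0.90 and margin 0.09, one-sided alpha 0.025, ICC 0.01 or 0.02 (all Section 11.2); 83% with two or more conditions, none with zero (Section 2.1); mean age 74, entry at 62 or older (Section 4.1).

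**Assumed, because the documents do not give them.** The SD of age (5–10 years) and the shape of the condition count.

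**Step 1: the plan's own power.** There is no stated figure for the moderator tests, so the nearest check is the main power. Evaluable per arm = 275 × 0.85 = 233.75; site size after dropout = 21.25; effective n at ICC 0.01 = 233.75 / (1 + 20.25 × 0.01) = 194.4. For pain, 8 / (25 × √(2/194.4)) = 3.15, and the noncentral t gives 88.2% (stated 89%). At ICC 0.02 it gives 82.9% (stated 83%). For arrest, an unpooled z gives 84.1% and 78.1% (stated 85% and about 80%). The inputs are read correctly, to within 2 points.

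**Step 2: information kept by a cut.** If the treatment effect is linear in a moderator X and the model uses a binary D instead, the information for the interaction is multiplied by r², the squared correlation of X and D.

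*Age at 75.* For a normal variable cut at proportion p, r² = φ(z_p)² / [p(1−p)]. At the median this is 0.3989² / 0.25 = 0.637. Splits from 40% to 55%, and skewed or truncated ages (minimum 62, mean 74, SD 5–10), give 0.62–0.68 kept, so 32–38% is lost.

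*Two or more conditions, 83/17.* A worked case is count = 1 + Poisson(λ) with P(count = 1) = 0.17. Then λ = −ln 0.17 = 1.772, the variance is 1.772, and the covariance with the split is 0.17 × 1.772 = 0.301. So r² = 0.301² / (1.772 × 0.83 × 0.17) = 0.363. Other shapes anchored to the same 17%:

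| Assumed shape | Kept | Lost |
|---|---|---|
| Normal latent burden | 0.45 | 55% |
| Binomial(10) | 0.43 | 57% |
| Zero-truncated binomial(10) | 0.39 | 61% |
| Poisson | 0.385 | 61.5% |
| 1 + Poisson | 0.36 | 64% |
| Zero-truncated Poisson | 0.34 | 66% |
| 1 + negative binomial | 0.30–0.34 | 67–70% |

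The untruncated Poisson and binomial put about 3–4% at zero conditions, which Section 2.1 contradicts. Removing the zeros makes the loss slightly larger.

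**Step 3: what this means for power.** Suppose the linear interaction would have 80% power (two-sided 0.05). With the cut it has Φ(2.80 × √r² − 1.96): about 60–64% for age and about 33–47% for conditions. Equivalently, 550 people carry the information of about 341–374 (age) or 165–250 (conditions).

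**Step 4: the smaller cell.** 0.17 × 275 × 0.85 = 39.7 per arm. Half-widths before clustering are 1.96 × 25 × √(2/39.7) = 11.0 on pain and 1.96 × √(2 × 0.09/39.7) = 0.132 on arrest. The 40 extra participants added for COVID-19 change little: 0.17 × 590 × 0.85 / 2 = 42.6 per arm, and a pain half-width of 10.6.

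**Step 5: the larger cell.** 0.83 × 275 × 0.85 = 194 per arm. Half-widths are 5.0 and 0.060 before clustering, or 5.4 and 0.064 with ICC 0.01.

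**The case against.** The case against is substantial, and much of it stands.

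- **The plan is not committed to a binary age.** A reader might infer that it is, but the split is an example inside a list of examples. The comorbidity coding is also listed as an example, though it offers no alternative. The plan does not split everything either: Table 8.1.1 treats oral health behavior and symptoms as scores.
- **Age in years is inferred.** It follows plausibly from the entry age and the cut at 75, but it is not stated.
- **The loss depends on a graded effect.** If the effect truly steps at the cut, the binary term loses nothing and a linear term is the worse choice. The documents give no reason to expect a step at 75 or at two conditions.
- **The emphasized subgroup is well estimated.** Section 2.2 concerns people with co-existing conditions, closer to the 83% than the 17%. Step 5 shows that cell's half-widths are well inside both margins. This does not help the interaction test, which depends on the small cell.
- **Two stronger readings fail.** One might conclude that the small subgroup cannot show non-inferiority. With identical arms the chance before clustering is about 29–30% on pain and 27% on arrest, which is low but not zero, and Section 11.4 plans no non-inferiority test in subgroups. One might also call the test nearly blind to a graded effect; keeping 30–45% of the information is a serious loss, but not blindness.
- **Other analyses might help.** The tree is secondary and its coding of moderators is unstated. The sensitivity analyses vary the covariates in the GEE models but do not promise uncut moderators.

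**Conclusion.** The point holds as an improvement to a supportive analysis. For a graded effect, the two-or-more coding loses roughly 55–70% of the interaction information and the example age split roughly one third. No single percentage covers both moderators. The figures rest on linearity of the effect, on assumed distributions for the count and for age, and on the 83% from an earlier survey rather than from trial participants with caries. The primary non-inferiority conclusion does not depend on any of this.

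**What to change.** In the heterogeneity paragraph of Section 11.4, name treatment-by-age in years and treatment-by-number-of-conditions (from the 10-item checklist) as the main interaction tests. Fit each as linear, with a spline or other non-linearity check. Report the treatment effect with its 95% CI at fixed values, for example ages 65, 75 and 85, and one, three and five conditions. Keep the two-group intervals for display. State whether the tree will receive the full values, and confirm that age is recorded in years.

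The cost is plan wording only: no new data and no change to the primary analyses. The downside is a linearity assumption, which the non-linearity check is there to test.

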## 12 SOURCE DOCUMENTS AND ACCESS TO SOURCE DATA/DOCUMENTS

Study staff will maintain appropriate research records for this study, in compliance with ICH E6, Section 4.9 and regulatory and institutional requirements for the protection of confidentiality of subjects. CWRU will permit authorized representatives of PCORI, and regulatory agencies to examine (and when required by applicable law, to copy) research records for the purposes of quality assurance reviews, audits, and evaluation of the study safety, progress, and data validity.

All records with identifiable information will be kept in secured locked storage units or stored in secure online databases. Only local (i.e. study staff) at CWRU and PCORI staff appointed to the trial will have access to the records. Access by the PCORI staff is for the purposes of quality assurance reviews, audits, and evaluation of the study safety and progress.

### Specific original documents and data records include, but are not limited to:

- **Participant Consent chart** contains all participant-identifying information. The chart includes the signed consent form, Consent Documentation form, the Contact Info form, Unanticipated Problem or Serious Adverse Event forms, Telephone Contact log and Reimbursement form. These documents will contain the participant's name and other confidential information (i.e. names of family members). (Electronic and Paper Based)
- **Participant Research chart** includes Case Report Forms (CRFs) and the Progress Notes Checklist. Examples are: ICDAS caries dental assessment form ; and Participant Questionnaire (Electronic and Paper Based). Medical information for chronic illnesses will be from participant self-report.
- **Tracking logs (in RedCap)** (Electronic)
- **Memoranda** (paper-based)

Some case report forms will be completed by study staff (Research Assistants, the Research Associate, or Project Coordinator, depending on the event). Exceptions will be the Participant Questionnaires, Contact information and Consent form(s) that will be completed by the Participant. The study staff will complete all provider audit forms. Data will be handled in accordance with GCP, U.S. federal regulations, local regulations (if applicable), and instructions from PCORI. All essential documents should be filled out completely and signed by the study staff collecting or recording the data. When necessary, essential documents (like consent/assent forms) will be reviewed, signed and dated by the principal investigators or study staff designated by the principal investigators.

## 13 QUALITY CONTROL AND QUALITY ASSURANCE

### 13.1 Definitions

#### **Quality Assurance (QA)**

The process to ensure the quality of the intervention meets the study design expectations.

#### **Quality Control (QC)**

A set of routine technical activities to measure and control the quality of the intervention and accuracy of data acquisition as the intervention is being implemented.

### 13.2 Study Intervention and Study Questionnaires

#### **13.2.1 Quality Assurance Procedures**

##### ***Study Staff:***

Study staff who will recruit and interact with participants at the facilities, and document study activities will attend in-person training which will incorporate the topics of human subject protection, Good Clinical Practice (GCP), and adherence to the study protocol. As part of tracking and managing study records, staff members will learn how to document activities that occur with subjects, update study documentation and use the tracking and audit logs. To assess proficiency, the study staff will be certified in the topics presented to ensure their comprehension of the expectations.

In addition, all study staff will be trained to make calls during the dedicated staff training. A script for each type of call will be created in REDCap and study staff will practice during training until they are proficient in utilizing the script and recording the call details.

Additionally, the dental hygienists will undergo calibration exercises prior to the main study to become proficient in exam related study procedures and to maintain intra- and inter-examiner agreement. Dentist experts in the application of SDF, ART, and FV will train and calibrate the dental hygienist and study dentist in the clinical protocol during a two day training session. Additionally, a gold standard examiner will calibrate/train the examiners in the ICDAS protocol in a separate 4-day training session. Detailed clinical and caries assessment training, calibration and reproducibility protocols are in the attached training protocol. Hygienists will not utilize dental radiographs. At the 26-week and 52-week exams, the hygienists will not have access to the results of the baseline examination to avoid detection bias.

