## 4 STUDY DESIGN

This study is a cluster randomized clinical trial to assess the comparative effectiveness of two caries treatment interventions for individuals residing in 22 publicly subsidized housing facilities/sites (HUD Section 202) and other low-income housing voucher programs in NE Ohio (**RQ-2**). Each facility will be randomized to 2 arms:

Arm 1 (11 facilities) – A total of 275 participants from these facilities will receive biannual SDF.

Primary Hypothesis: Simple medical treatment (Arm 1) is non-inferior to typical dental treatment (Arm 2) for clinical (caries arrest) and patient-reported (tooth pain/hypersensitivity) at 12-months post treatment.

Arm 2 (11 facilities): A total of 275 participants from these facilities will receive ART + biannual FV application.

Secondary Hypothesis: Simple medical treatment (Arm 1) is non-inferior to typical dental treatment (Arm 2) for clinical (new decay) and patient-reported (oral health quality of life) outcomes at 12-months post treatment.

The participants will be recruited over a *three*-year period, and each participant will be followed for one year (total of 3 visits -baseline, 26 weeks, 52 weeks). All participants will receive a dental screening and prophylactic cleaning at all visits. The proposed interventions will address the high burden of untreated tooth decay in community dwelling low-income older adults and thus reduce disparities (**RQ-5**). The non-surgical interventions can be provided by paraprofessionals. We have previously worked in these housing facilities and understand the logistics of recruiting and conducting clinical dental exams on-site (**PC-1**).

The randomization is at the level of the cluster (housing facility) for logistical efficiency. This will greatly reduce the potential for error that could otherwise occur with people at the same site assigned to different treatments. Furthermore, keeping the same treatment at each site reduces chances of 'contamination' (i.e. participant discussing their treatment with others). Additionally, stratified cluster randomization will be used, i.e. a block (constrained) randomization approach in which balance over treatments is assured for 2 key cluster-level (stratification) variables, namely facility size ( $>100$  versus  $\leq 100$  residents), and geographic location (Cuyahoga County vs other (**RQ-5, RC-2, RC-5**)).

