## **7.2 26-Week Visit (T26) (Day 168 to Day 196)**

### **Dental Exam and Treatment**

- Dentists will administer the Safety Questionnaire (Pre-Exam).

- Hygienists will perform dental examination at participant's respective housing facility to evaluate caries arrest and identify new decay.
- Study staff will record results of dental examination.
- Hygienists, under the direction of the study dentist, will administer the intervention treatment (based on study arm) for all previously treated lesions and newly identified active root or coronal carious lesion with ICDAS-II lesion severity code of 3 or greater.
- Study staff will give participants referral sheets with exam results and direction to follow up with their personal dentist for routine dental care.
- If a participant reports any issue with the applied treatment within one week of the treatment date, the study team will return to the housing facility to examine and correct the treated tooth as needed. Within 48 hours, the study team will call the participant to ask the participant if the issue has been resolved and will administer a paper safety questionnaire. The completed paper safety questionnaire will be stored in the CRF folder and documentation of the return visit/treatment will be added to the participant's electronic record.

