### **7.3 52-Week Visit (T52) (Day 365 to 379)**

#### **Dental Exam and Treatment**

- Dentists *or* hygienists will administer the Safety Questionnaire (Pre-Exam).
- Hygienists will perform dental examination at participant's respective housing facility to evaluate caries arrest and new decay.
- Study staff will record results of dental examination.
- Study staff will give participants referral sheets with exam results and direction to follow up with their personal dentist for further treatment or routine dental care.

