### 8.1.1 Quantitative outcomes of interventions

The primary (i.e., caries arrest, tooth pain / sensitivity) and secondary outcomes (i.e., presence of new decay, oral health-related quality of life) measure the effectiveness of the study interventions. The process outcome are to access the safety of the interventions and to ascertain patient satisfaction with the treatment 1 year after the initial treatment.

**Primary outcome: Older adults caries arrest and tooth pain / sensitivity (Arm 1: SDF vs. Arm 2: ART + FV) will be assessed through:**

- Clinical dental exam: will be performed at the two intervention time points (T0, T26) and final time point (T52) by a trained and calibrated dental hygienist according to the International Caries Detection and Assessment System II (ICDAS-II). The exam will be used to identify a change in oral health status between the Baseline visit and the 26-week visit (T0 and T26) as well as the 26-week visit and the 52-week visit (T26 and T52).
- Self-reported evaluation: Scales on tooth pain / sensitivity (PROMIS v.1.0, Health Organization; Dental Discomfort Questionnaire (DDQ)) will be used to measure levels of change in oral pain / sensitivity improvement. Higher scores on the PROMIS and DDQ

indicate increased tooth pain / sensitivity. These measures will be conducted during the baseline visit, 26-week visit, and 52-week visit ( $T_0$ ,  $T_{26}$ , and  $T_{52}$ ).

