**Secondary outcomes: Older adults' new decay and GOHRQoL (Arm 1: SDF vs. Arm 2: ART +FV) will be assessed through:**

- Clinical dental exam: A newly carious tooth is defined as any tooth receiving an ICDAS lesion code  $\geq 3$  that received a sound code on the previous dental exam or any tooth surface with an ICDAS filling code  $\geq 3$  that previously did not have one. The number of teeth with new decay or filling will be assessed through clinical dental exams ( $T_0$ ,  $T_{26}$ , and  $T_{52}$ ) and recorded on the ICDAS Assessment form.
- Self-reported evaluation: The Geriatric Oral Health-related Quality of Life (GOHRQoL) consist of 12 questions and will be used to assess the impact of the intervention on participants overall oral health quality of life. The overall score will be calculated with higher scores indicating that the participant has greater oral health Quality of Life. The measures will be collected within two week of the baseline visit, the 26-week visit ( $T_0$ ,  $T_{26}$ ), and 52-week visit exam ( $T_{52}$ ).

**Process outcome: Safety and satisfaction and moderating variables (Arm 1: SDF vs. Arm 2: ART +FV) will be assessed through:**

- The Safety Questionnaire-Revised for Adults consists of 15 main adverse events (i.e., existence of dental insurance, severity of adverse symptoms after receiving the dental treatment) and will be used to identify adverse events. Participants will complete this survey pre- and post-exam/treatment at the baseline visit, 26-week visit, and the 52-week visit, respectively. The treatment satisfaction will be assessed through the treatment satisfaction questionnaire for medication (TSQM) modified for Dental and satisfaction with new treatment for cavities, comprised of six questions. The overall average score will be assessed from these two scales with higher mean score indicating better satisfaction with the study treatment. The measures will be conducted during the baseline visit, follow-up visit, and final exam ( $T_0$ ,  $T_{26}$ , and  $T_{52}$ ).

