### **13.2.2 *Quality Control Procedures***

#### ***Study Staff:***

Data quality control is primarily conducted at the study team level through internal processes of data review/data monitoring as the data is collected and through periodic custom reports (See Table 16.4.1). Dental exam data will be reviewed for accuracy and completeness after each study visit by the Dental Hygienist. The Study Staff will review the questionnaires after the participants have completed them. Each paper form and questionnaire will be entered and verified by two separate individuals. Forms completed electronically via tablets will be checked by study staff prior to leaving the facility. Any field that is unclear will be clarified with the participant who completed the document.

All study forms and questionnaires collected and entered into the database will be checked for inconsistencies and range and assessed for missing data. Any inconsistencies, outliers, or missing data observed will be compared to the paper document and appropriate corrective actions carried out. REDCap's native data resolution workflow will be used to document and fix any data anomalies. The Data Manager will also respond to data queries generated by the PI, Study Coordinator, or other study staff.

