### 15.3 Types of Data Collected

Participant data for this study will include: (1) dental exam data, (2) study questionnaires and (3) intervention tracking data. Additionally, audio recordings will be used for fidelity monitoring. A summary of the types of data collected, the storage location and the methods of completion can be seen in Figure 15.3.1.

Figure 15.3.1			
Mail Clinical Trial			
Storage Location	Form/ Questionnaire	Type	Method of Completion
Consent Folder and REDCap	Consent Form	Consent	

▪ Direct Entry by Participant and study staff into RedCap via Tablet

▪ Paper Form

Consent Folder and REDCap	Consent Documentation	Consent	

▪ Direct Entry by study Staff into RedCap

▪ Paper Form

Consent Folder and REDCap	Participant Contact Form	Contact	

▪ Direct Entry by Participant into RedCap

▪ Paper Form

CRF Folder and REDCap	Screening and Eligibility Form	Screening and Eligibility	

▪ Direct Entry by study Staff into RedCap

▪ Paper Form

CRF Folder and REDCap	Participant Questionnaire A	Demographics, Medical History, Oral Behavior and Oral Health Symptoms	

▪ Direct Entry by Participant and study staff into RedCap

▪ Paper Form

CRF Folder and REDCap	Participant Questionnaire B	Tooth Pain/Sensitivity and Oral Health Quality of Life	

▪ Direct Entry by Participant and study staff into RedCap

▪ Paper Form

CRF Folder and REDCap	Safety Questionnaire (Pre-Exam) and Participant Questionnaire C	Safety	

▪ Direct Entry by study staff into RedCap

▪ Paper Form

CRF Folder and REDCap	Participant Questionnaire D	Satisfaction	

▪ Direct Entry by study staff into RedCap

▪ Paper Form

CRF Folder and REDCap	Intervention Delivery Tracking	Treatment Log	

▪ Direct Entry by study staff into RedCap

▪ Paper Form

CRF Folder and REDCap	Dental Exam Forms	Oral Health Screening and Carries Arrest and New Decay	

▪ Direct Entry by study staff into RedCap

▪ Paper Form

Focus Groups			

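### Section 13.2.1 withholds only the baseline results at follow-up exams; the rule should also cover the week-26 record at the deciding week-52 exam and be reconciled with Section 7.2

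*Combined protocol and SAP*

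**What the plan says.** Section 13.2.1 (Quality Assurance Procedures, Study Staff) states the safeguard: "At the 26-week and 52-week exams, the hygienists will not have access to the results of the baseline examination to avoid detection bias". It is the only sentence in the documents that limits examiners' sight of earlier exam results. It names one exam and one role.

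The arrest outcome is decided at 12 months. Section 4 opens its primary hypothesis with "Simple medical treatment (Arm 1) is non-inferior to typical dental treatment (Arm 2) for clinical (caries arrest" and sets that time point. Section 7.3 says who scores it: "Hygienists will perform dental examination at participant's respective housing facility to evaluate caries arrest and new decay". Section 8.1.1 reads change between baseline and week 26 "as well as the 26-week visit and the 52-week visit", and counts as newly carious a tooth with a lesion code of 3 or more "that received a sound code on the previous dental exam". For week 52, the previous exam is week 26.

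Figure 15.3.1 places the dental exam forms and the treatment log ("Intervention Delivery Tracking") in the CRF folder and REDCap. Sections 7.1 to 7.3 have study staff record the exam. The temporary COVID-19 clinical protocol in Section 7 has a recorder chart while the hygienists examine, and a dentist check the charting.

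Section 7.2 has the hygienists give the week-26 intervention "for all previously treated lesions and newly identified active root or coronal carious lesion" at or above the severity threshold.

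**The concern.** The sponsor saw that knowing earlier results can colour a follow-up score and wrote a rule against it. At week 26 that rule covers the only earlier exam. At week 52 it covers the older of two and is silent on the more recent one, which holds each lesion's latest status. The silence falls at the visit that decides a primary non-inferiority outcome.

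Arrest is also sensitive to single lesion scores. Section 11.2 counts a person as arrested only if every lesion is arrested, so one lesion score carried over from an earlier chart can change that person's result. Visible stain or a filling tells an examiner that a tooth was treated. It does not tell how the previous examiner scored it; a chart does.

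The rule also meets a practical problem in Section 7.2. To treat previously treated lesions at week 26, someone must know which they were, and the plan does not say who supplies that list or when it is opened.

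**Working it through.** **Coverage of the rule, visit by visit**
- Week 26: the earlier record is the baseline exam. Section 13.2.1 withholds it from the hygienists.
- Week 52: the earlier records are baseline and week 26. Section 13.2.1 withholds baseline. No section withholds week 26.
- Treatment log: no section withholds it expressly. Under Section 7.1 every active lesion with code 3 or more is treated at baseline, so a log that lists treated lesions (its content is not shown) would reproduce much of the baseline finding that 13.2.1 withholds.
- Roles: the rule names hygienists. It does not name the recorder, or the dentist who checks charting under the COVID-19 protocol. Sections 6.8 and 6.11 say the dentist may be absent at week 52, so the dentist matters mainly at week 26.

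**Section 13.2.1 against Section 7.2 at week 26**
- If the bar lasts the whole visit, the hygienists cannot learn from the baseline results which lesions were treated, and Section 7.2 rests on what is visible in the mouth or on a list from an unnamed source.
- If the bar lasts only until the exam is done, both sections can be followed, but the moment at which the list opens must be written down.
- Section 5.4.2 places assessment before intervention at all treatment visits. That fixes the order of the procedures, not the moment of access.

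**Does scoring need the earlier charts?** Section 8.1.1 defines comparisons between visits. Section 13.2.2 gives longitudinal coding of the dental data to the Data Manager after collection. Withholding charts therefore costs the scoring nothing.

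**Arithmetic: the plan's own power figure.** Inputs from Section 11.2: 275 per arm, 15% dropout, 25 per site, ICC 0.01 (0.02 as the alternative), 90% arrest in both arms, margin 0.09, one-sided alpha 0.025.
- Analysed per arm: 275 × 0.85 = 233.75; per site: 25 × 0.85 = 21.25.
- Design effect at ICC 0.01: 1 + 20.25 × 0.01 = 1.2025; effective n = 233.75 / 1.2025 = 194.4. At ICC 0.02: 1.405 and 166.4.
- SE = √(2 × 0.9 × 0.1 / 194.4) = 0.0304; power = Φ(0.09/0.0304 − 1.96) = 84.1%. At ICC 0.02, 78.1%. The plan states 85% and about 80%, so both reproduce within 2 points.

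**Illustration of anchoring.** Assumptions that are not in the documents: true week-52 arrest is 81% for SDF and 90% for ART + FV (a deficit equal to the margin), ART + FV is also at 90% at week 26, and a share q of person-level week-52 results is carried forward from week 26.
- Observed SDF rate = (1 − q) × 0.81 + q × (SDF rate at week 26). With d this rate minus 0.90, the chance of concluding non-inferiority is Φ((d + 0.09)/SE − 1.96).
- SDF at 90% at week 26, q = 20%: rate 0.828, d = −0.072, SE = √((0.09 + 0.828 × 0.172)/194.4) = 0.0346, chance = Φ(0.018/0.0346 − 1.96) = 7.5%.

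| q | ICC 0.01 | ICC 0.02 |
|---|---|---|
| 0 | 2.5% | 2.5% |
| 10% | 4.4% | 4.3% |
| 20% | 7.5% | 7.0% |
| 25% | 9.6% | 8.8% |

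- SDF already at 81% at week 26: the observed rate is 0.81 for any q, and the chance stays at 2.5%.
- SDF at 75% at week 26, q = 20%, ICC 0.01: rate 0.798, d = −0.102, SE 0.0360, chance = Φ(−0.012/0.0360 − 1.96) = 1.1%, a fall.

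The sign of the effect depends on the unknown week-26 gap, and its size on the unknown q.

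**The case against.** The strongest reply is that silence is not access. Section 15.6 keeps paper files at the university in locked cabinets, with keys held only by the Data Manager and the PI. Section 15.2.2 tests that each REDCap role sees only what it is entitled to. Section 5.4.2 says hygienists go to the facilities unaware of assignment, which an open treatment log would defeat. It also swaps the examiner pairs at 6 months, says 12 months will be handled similarly, and has 20% of participants randomly re-examined. Section 13.2.1 requires calibration and refers to a training protocol that is not among the published documents and may hold a fuller rule.

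Most of this stands. A reader might infer that the week-26 chart and the log lie open to the week-52 examiner; the documents do not say so, and these provisions point the other way. Storage of exam forms and log in the same places shows only where they are kept.

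It does not close the gap. Section 15.6 governs storage, not what is carried to a facility. The hygienist role in REDCap is not described, and Section 11.4 has dental assessments on paper. Rotation limits hygienists evaluating their own work; it does not stop one reading a colleague's score, and the direction of the 12-month swap is not given.

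Two further inferences should be set aside. Section 13.2.2 says "Dental exam data will be reviewed for accuracy and completeness after each study visit by the Dental Hygienist", which might suggest that week-52 scores could be revised after treatment; no treatment is given at week 52, so that cannot arise there. And a reader might conclude that anchoring must favour non-inferiority. It does so only if the gap between the arms was smaller at week 26 than at week 52. Scores carried forward as active would understate arrest.

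**Conclusion.** The concern holds as an incomplete safeguard. The plan's only rule on examiners' sight of earlier exams does not reach the week-26 record at the week-52 exam, does not name everyone involved in charting, and has to be reconciled with the week-26 treatment instruction in Section 7.2. These points rest on the text alone.

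No breach is shown, and no bias of known size or direction follows. The false non-inferiority figures of 4.4% to 9.6% at ICC 0.01 rest on an assumed q of 10% to 25%, arms equal at week 26, and a true loss of 9 points for SDF alone by week 52. They show that the gap could matter, not that it does. Sample size, power and nominal alpha are unaffected. Closing the gap would reduce anchoring on earlier scores; it would not mask the arm where stain or fillings are visible.

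**What to change.** - **Section 13.2.1:** in place of the baseline results alone, withhold *the results of any earlier examination or the treatment log*. Apply this to the hygienists, the recorder and any dentist who checks the charting, until the current exam form is complete, and to paper charts as well as REDCap.
- **Section 7.2:** state that the list of previously treated lesions is opened only after the week-26 exam has been recorded, and that later changes to that form are limited to logged transcription corrections. This concerns only when information is seen, not which lesions are treated.

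The Section 13.2.2 review can stay where it is.

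The cost is a few sentences, a REDCap rights setting, a matching rule for paper forms, and a brief step at each visit to close the exam form before the list is opened. It needs no extra staff and no change to sample size or analysis.
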